Our group has previously demonstrated that IBD patients are at increased susceptibility for developing CDI and clinical outcomes of CDI in the IBD patient population are overall worse, with increased morbidity and mortality(5)(6). This work was performed prior to the advent of enhanced immunotherapeutics targeting *C difficile* toxins (i.e. bezlotoxumab) (7). Due to the need for uniformity in the short term clinical response to anti-*C difficile* therapy, and a clinical read out emphasizing diarrhea resolution, IBD patients were excluded from many of the pivotal trials on new agents for the treatment and prevention of CDI over the past decade. This was necessary as CDI will frequently trigger a “flare” of underlying IBD related inflammation, which will make interpretation of *C. difficile* treatment too difficult. As a result of this pragmatic trial necessity, there is very limited data regarding the effectiveness, tolerability and long-term impact of these newer agents on a high risk population of patients, who would theoretically have the most benefit from improved CDI treatment. This lack of evidence has unfortunately been used as a barrier, preventing IBD patients from gaining access to enhanced CDI treatment. Thus a “Catch-22” scenario has emerged, where IBD patients, who suffer from complex and severe CDI which frequently precipitates flare of their underlying IBD, where excluded from the pivotal trials (out of necessity), but the resulting lack of evidence now functions as a barrier to their ability to receive these more effective, albeit more costly upfront treatments.

This proposal seeks to address this knowledge gap by specifically treating IBD patients with *C difficile* antibody approaches to demonstrate effectiveness as well as improved long-term outcomes and overall cost-effectiveness.

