In order to demonstrate an improved long-term natural history following enhanced *C difficile* therapy in IBD, our group had to first demonstrate the natural, multiyear history of CDI on patients with IBD using existing treatment modalities. Our recently published manuscript characterizing the long-term natural history of IBD following CDI clearly demonstrates that the underlying IBD accelerates in many of the patients experiencing this infection. This project, performed with the support of an investigator initiated study (IIS) from Merck, used a propensity score matching strategy to determine an appropriate IBD control population to assess the impact of CDI over the year of infection and the year following infection. This work led to important insights regarding CDI in IBD(5). The propensity score matching was performed in the year preceding the CDI, and the matching was carried out for 24 criteria known to be relevant for the development of CDI. IBD patients at risk for CDI were in general sicker than the average patient, with higher rates of steroid exposure, hospitalization and antibiotic exposure, compared with the

average patient in the clinic. As expected, *C difficile* exerted a negative effect on the natural history of IBD and is associated with an increase in IBD severity and healthcare utilization. During the year of CDI, IBD patients had an increased objective evidence of inflammation, increased disease activity scores and lower quality of life scores when compared to those who did not have CDI. Most importantly, we demonstrated that within this vulnerable population, CDI has a long lasting, negative effect on patient clinical trajectories, which was clearly evident in the year after infection. IBD patients with CDI continued to require antibiotics and demonstrated a 6 fold increase in healthcare charges compared with matched individuals who did not experience CDI. IBD patients with CDI generated mean healthcare charges (irrespective of pharmacy charges) of \$48,000 annually, compared with an expected median charge of \$7,000 in the matched control population.

Thus, we proposed to prospectively assess the short and long-term impact of enhanced CDI therapy in the IBD patient population with Bezlotoxumab. Having defined the natural history of CDI over a 2 year time period, we will use an identical structure to determine if there is an improvement in clinical trajectory with enhanced CDI therapy the year after infection.

3. Study Design:

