This is a prospective, single center, non-randomized, observational, open label study to compare tolerability, efficacy, and short and long term clinical outcomes of Bezlotoxumab in CDI IBD patients.

A total number of 50 patients will be enrolled. Patients who agreed to receive Bezlotoxumab will be compared to our recently published historical controls as well as IBD registry patients who do not elect to receive enhanced *C difficile* therapy.

Patient population will include any patient who receives care at the Digestive Disorder Center at UPMC Presbyterian Hospital.

Inclusion criteria: >18 years old, diagnosis of IBD and CDI.

Exclusion criteria: <18 years old, no IBD, no CDI, history of colectomy.

4. Study Flowchart

Data collection:

Visit 1 (Enrollment)

- a. Demographic information
- b. type of IBD
- c. disease duration
- d. history of bowel resection
- e. current medications
- f. inflammatory markers: CRP, ESR, Albumin
- g. CBC
- h. quantitative immunoglobulins
- i. Vitamin levels (Vit D and Vit B)
- j. Disease related quality of life (SIBDQ)
- k. Disease activity scores (HBI-UCAI)
- l. Dietary intake (sugar and fat intake)

m. Stool sample

Visit 2 (90 days after enrollment)

Clinic visit or Telephone call

- a. inflammatory markers: CRP, ESR, Albumin (if available as a standard of care)
- b. CBC (if available as a standard of care)
- c. Disease related quality of life (SIBDQ)
- d. Disease activity scores (HBI-UCAI)
- e. ED visits
- f. Hospital admissions

Visit 3 (1 year after enrollment)

Clinic visit or Telephone call

- a. inflammatory markers: CRP, ESR, Albumin (if available as a standard of care)
- b. CBC (if available as a standard of care)
- c. Disease related quality of life (SIBDQ)
- d. Disease activity scores (HBI-UCAI)
- e. ED visits
- f. Hospital admissions

Visit 4 (24 months after enrollment)

Clinic visit or Telephone call

- a. inflammatory markers: CRP, ESR, Albumin (if available as a standard of care)
- b. CBC (if available as a standard of care)
- c. Disease related quality of life (SIBDQ)
- d. Disease activity scores (HBI-UCAI)
- e. ED visits
- f. Hospital admissions
- g. Total charges associated with cost of care

5. Study Procedures:

This is a prospective observational study comparing the effectiveness of Bezlotoxumab to reduce rates of CDI in patients with IBD. We will evaluate short and long-term clinical outcomes after treatment with Bezlotoxumab.

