Patients who are part of the IBD Registry and have a defined IBD diagnosis and CDI will be approached to be consented for this study. Randomly the study treatment will be offered to 50 patients.

Diagnosis of CDI will be accomplished using the standard CLIA certified strategies employed in our microbiology/virology clinical laboratories, which include PCR amplification, two step GDH /gene amplification of liquid/unformed stool samples.

Patients will be divided into 2 groups of treatment and followed in a parallel fashion for the next 2 years: 1. Those who agree to receive Bezlotoxumab (Case) and 2. Those who do not agree to received Bezlotoxumab (controls).

6. Study Duration:

Total duration time: 5 years. 36 months enrollment and 24 months follow up.

7. Statistical Analysis and Sample Size Justification:

Sample size: 50 (Based on the prevalence of CDI within our patient population)

Descriptive statistics of baseline characteristics will be used to characterize the 50 IBD CDI patients who agree to receive Bezlotoxumab. The baseline characteristics under consideration include demographic data, type of IBD, duration of IBD, current medications, inflammatory markers, SIBDQ, HBI-UCAI and others collected at the time of enrollment. Mean, standard deviation, median and interquartile range will be reported on continuous variables and proportions reported on discrete variables.

Similar baseline characteristics will be collected at enrollment among historical controls and IBD registry patients who do not elect/ not offered to receive enhanced C difficile therapy. Similar descriptive statistics will be used to characterize these controls. A logistic regression model will be developed to predict the status of receiving Bezlotoxumab from the extensive list of baseline characteristics. Subsequently each study participant, including both the 50 patients who receive Bezlotoxumab and the controls, will be assigned a predicted probability of treatment based on this propensity score model. The inverse probability weighting method will be used to compare the Bezlotoxumab-treated IBD CDI patients and the controls in baseline characteristics to demonstrate balanced baseline characteristics between the two groups after inverse probability weighting (8).

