In the primary analysis, we will compare the risk of recurrent CDI between the 50 treated and 118 controls at 90 days after enrollment. The inverse propensity score-weighted method will be used to estimate the proportion of recurrence CDI at 90 days under Bezlotoxumab among IBD CDI patients seen in the clinics and compared with that for IBD CDI patients without Bezlotoxumab. Other long-term outcomes for comparison include, number of healthcare utilization (emergency room visits and hospitalization), overall charges during the second year after the study enrollment; inflammatory markers and CBC (in continuum and binary: abnormal vs normal), SIBDQ, HBI-UCAI, dietary intake at the 90 days, 12-month and 24-month visits. The inverse probability-weighted method will be used to compare these outcomes between Bezlotoxumab-treated and controls with IBD CDI. Cardiac failure will be closely monitored throughout this study and the proportions of cardiac failure among the 50-treated patients by the first 90 days, 12 months and 24 months will be estimated. The paired t-test or the nonparametric signed-rank test will be used to test the change baseline to the 24-month visit in continuous outcomes and the McNemar test will be used to for discrete outcomes.(9)

Using data from the 50 IBD CDI patients, linear-mixed models and generalized linear-mixed models will be used to explore the longitudinal change in the repeatedly measured assessments of disease activity and quality of life, including current medications, inflammatory markers, annual overall financial charges, annual use of healthcare facilities (such as emergency room visit and number of hospitalizations) SIBDQ, and HBI-UCAI. Trajectory analyses on these multiple longitudinal patient outcomes will be used to identify IBD CDI patients who have responded to the treatment and who have not. Subsequently we will compare the baseline patient characteristics between the treatment responders and non-responders and the results will be invaluable in guiding future management of IBD CDI patients.

Based on data from 28 IBD CDI patients, it was reported that the proportion of IBD patients with recurrent CDI within 12 weeks of follow-up was 26.7% among Bezlotoxumab-treated and 53.8% among those without Bezlotoxumab (10-11). With 118 controls and 50 Bezlotoxumab-treated patients, we will have 88% power to detect the same difference by using the Fisher's Exact test with a 2-sided alpha level at 0.05.

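### The uncontrolled tests of change from enrollment to 24 months cannot separate a drug effect from recovery after CDI

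*Combined protocol and SAP*

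**What the plan says.** Section 7 (Statistical Analysis and Sample Size Justification) states: "The paired t-test or the nonparametric signed-rank test will be used to test the change baseline to the 24-month visit in continuous outcomes". The same sentence adds that "the McNemar test will be used to for discrete outcomes". It names no group and no comparator. It comes directly after the cardiac-failure estimates for the 50 treated patients, so its position suggests the treated group without saying so.

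The starting value is the one taken at Visit 1. Section 7 lists "SIBDQ, HBI-UCAI and others collected at the time of enrollment" among the baseline characteristics, and the Visit 1 list in section 4 adds CRP, ESR, albumin and CBC. Section 5 says that registry patients who "have a defined IBD diagnosis and CDI will be approached to be consented for this study". No interval from CDI diagnosis or treatment to Visit 1 is given.

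Section 2 describes these patients as having "complex and severe CDI which frequently precipitates flare of their underlying IBD". It also reports, from a comparison with matched patients who did not have CDI: "During the year of CDI, IBD patients had an increased objective evidence of inflammation, increased disease activity scores and lower quality of life scores".

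Section 7 separately plans inverse-probability-weighted comparisons of treated patients and controls for inflammatory markers, CBC, SIBDQ and HBI-UCAI at 90 days, 12 months and 24 months. A Hochberg procedure at familywise 0.05 appears in section 10 inside reference 9, which the paired-test sentence cites.

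**The concern.** A paired test asks whether the mean change is zero. In patients recruited during or soon after an infection that often provokes a flare, the mean change may differ from zero with no treatment effect at all. The episode resolves, and values that were high at selection tend to move back. If so, rejecting the null is statistically correct but says nothing about bezlotoxumab.

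The study hypothesis includes better long-term disease activity and quality of life, and these are among the measures tested. Section 7 does not say what the paired tests are meant to show. Its next paragraph uses trajectories in the 50 patients alone to decide who responded to treatment, so reading within-patient improvement as response is not far from the plan's own thinking. At stake is a reported improvement at 24 months that an inert drug could also have produced.

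**Working it through.** **The plan's own figure.** Section 7 states one power figure, 88%, for 90-day recurrence (26.7% against 53.8%, 50 treated, 118 controls, Fisher's exact test, two-sided 0.05). A continuity-corrected sample-size formula at 88% power returns 50 treated, as stated. Full enumeration of Fisher's test gives 90.0%. The figure is reproduced approximately, but it does not bear on the paired tests, for which the plan gives no operating characteristics.

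**Inputs for the paired test.**
- Pairs: n = 50, the planned number treated. No dropout rate is stated, and follow-up markers are collected only if available from standard care, so n = 30 is shown as an assumed lower case.
- Drug effect: zero, by assumption.
- Natural recovery d: mean improvement divided by the SD of the change. The documents give no value, so a range from 0 to 0.5 is used.
- Change scores assumed normal.

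**Formula.** The paired t statistic follows a noncentral t distribution with n − 1 degrees of freedom and noncentrality d√n. The chance of significance is P(T > c) + P(T < −c), where c is the two-sided critical value. For n = 50 and alpha 0.05, c = 2.010. At d = 0.3 the noncentrality is 0.3 × √50 = 2.121, and the chance is 54.8%.

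| d | n = 50, alpha 0.05 | n = 30, alpha 0.05 |
|---|---|---|
| 0 | 5% | 5% |
| 0.1 | 11% | 8% |
| 0.2 | 28% | 19% |
| 0.3 | 55% | 36% |
| 0.4 | 79% | 56% |
| 0.5 | 93% | 75% |

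**What d means on the scale of the measure.** If enrollment values are shifted by k SD and the correlation between enrollment and 24 months is r, then d = k / √(2(1 − r)). With r = 0.5 the denominator is 1, so d = k. A shift of 0.25 SD gives significance 41% of the time at n = 50, and a shift of 0.5 SD gives 93%.

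**Hochberg adjustment.** The plan does not define the family. For an illustrative family of six, the strictest step is 0.05/6 = 0.0083. At n = 50 (c = 2.750) the chances at d = 0.3, 0.4 and 0.5 are 28%, 54% and 78%. At n = 30 they are 14%, 28% and 47%. Hochberg is less strict than this when several tests are significant together, so the adjusted rate lies between these values and the unadjusted ones.

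**A controlled comparison.** A simulation (20,000 replicates) compared change in 50 treated patients and 118 controls by a two-sample t-test, with the same natural recovery in both groups. At d = 0, 0.5 and 1 the rejection rate was 5.2%, 5.1% and 5.2%. Shared recovery cancels.

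**The case against.** A reader might infer that the plan itself places these measures at their worst at enrollment, so that the paired tests are bound to show improvement. The documents do not support that. Section 2 contrasts patients with CDI and matched patients without it over the year of CDI, which is not a within-patient low point. It says a flare is frequent, not universal. It also stresses lasting harm that was evident in the year after infection, and it gives no recovery figure. Baseline is enrollment, at an unstated distance from the CDI. A false improvement is possible, not certain.

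Three further points stand in part.
- The paired-test sentence never claims to show efficacy and names no group. That is true, but it plans formal tests and does not call them descriptive.
- Hochberg control lowers the rates. It does not cure the problem: if patients recover naturally, the no-change null is false, and control of false rejections does not apply.
- The controlled analysis is already planned. Enrollment values are available to the propensity model, and once weighting balances them, the 24-month difference between groups estimates the same contrast as the difference in change. What adding the enrollment value as a covariate gains is precision and protection against residual imbalance.

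The lasting harm described in section 2 is relative to patients without CDI, so it is compatible with partial recovery from the acute episode.

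**Conclusion.** The point holds in a limited form. The paired t, signed-rank and McNemar tests cannot distinguish a drug effect from recovery or regression to the mean, and the plan does not say that they are descriptive. The size depends wholly on a recovery that the documents do not give. With no recovery the test keeps its 5% rate. With 0.2 SD of the change and 50 pairs, an inert drug yields a significant result 28% of the time, and with 0.5 SD, 93%. These rates are unadjusted and assume normal change scores and complete pairs; fewer pairs or Hochberg adjustment reduce them.

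The primary 90-day recurrence comparison is not touched, and a controlled comparison of the same outcomes exists. The point is worth correcting before analysis but does not threaten the main result. The controlled comparison removes recovery only as far as recovery is shared, that is, as far as treated patients and controls are measured at a similar stage of the CDI episode.

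**What to change.** In section 7:

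1. State that conclusions about effect on 24-month outcomes come only from the planned inverse-probability-weighted comparison of treated patients and controls.
2. Add the enrollment value of the same measure as a covariate in that comparison where one was collected, using a logistic model for binary outcomes.
3. Replace the paired and McNemar tests with within-group change in each group, reported as estimates with confidence intervals and described as not testing a drug effect.
4. Report the planned weighted comparison without the covariate as well, because controls lacking an enrollment value drop out of the adjusted model.

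The cost is SAP wording. Similar enrollment data are already planned for controls, so no visit is added. The study gives up a test that is easy to pass, and the adjusted model may use fewer controls. Follow-up markers that depend on standard care remain incomplete under either approach. A comparison of 24-month values with values from before the CDI would be an optional addition only, since the documents do not show that the registry holds those data for these patients.
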